5.1.3. Treatment Period

During the treatment period, patients will treat their migraine attack with study drug. Patients who complete the assessment for their migraine attack treated by study drug will move to their EoS visit.

Patients will be instructed to treat their migraine attack within 4 hours of pain onset providing that the headache severity is at least moderate or severe at the time, is not improving, and no other migraine treatment has been taken. Patients will be required to record their response to the dose over the next 48 hours using the eDiary starting from prior to taking the drug (pre-dose), and at specific postdose time points of 0.5, 1, 1.5, 2, 3, 4, 24, and 48 hours.

For a migraine attack that does not meet the criteria above or when the patients are unable to treat with study drug and complete all study procedures during a particular migraine attack, they may use their usual migraine medication for that migraine attack and then treat the next appropriate migraine attack with study drug. When patients take their usual migraine medication (including antiemetic), there must be at least a 24-hour gap after taking the last dose of their usual migraine medication before treating the migraine attack with study drug. Details of migraine medication is provided in the concomitant medication/therapy list.

Patients should not take any other treatments for migraine until after completing the 2 hour assessments postdose. After that, patients requiring medication for rescue (the patient is not headache pain free at 2 hours), or for migraine recurrence (the migraine becomes pain free at 2 hours but then recurs after 2 hours), may take NSAIDs, acetaminophen, and/or antiemetic drugs with approved dosage and usage in Japan. The investigator should advise patients of appropriate medications to be taken for rescue and recurrence, and that triptans, ergots, opioids, and barbiturates MUST NOT be taken within 24 hours of study drug administration. The use of any rescue and recurrence medication other than study drug will be recorded in the patient's paper diary. The total time for recording response to study drug is 48 hours.

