To achieve between-group comparability, the randomization will be stratified (yes or no) for current use of concomitant medication(s) that reduce the frequency of migraine episodes.

At Visit 2, patients will be provided with study drug to treat a single migraine attack. Site personnel will confirm that they have located the correct investigational product by entering a confirmation number found on the investigational product into the IWRS before patients leave the site at Visit 2.

7.2.1. *Selection and Timing of Doses*

The actual time of dose administration will be recorded in the patient's eDiary. Patients will be instructed to take 3 tablets as the treatment for a new migraine attack, along with the following instructions:

- The migraine must be at least of moderate or severe severity.
- The migraine must be treated within 4 hours of pain onset.
- No prior analgesic or acute migraine treatment within 24 hours of study drug administration has been taken to treat the current migraine attack.

7.2.1.1. *Rescue/Recurrence Medication*

Rescue medication will be permitted after completion of the 2 hour assessments if the migraine does not respond with study drug (patient is not headache pain free). If the migraine does not respond within 2 hours, a rescue dose of NSAIDs, acetaminophen, and/or antiemetic drugs may be taken after completion of the 2 hour assessments of the study drug dose. Triptans, ergots, opioids and barbiturates MUST NOT be used for rescue medication within 24 hours of study drug administration.

If the migraine responds within 2 hours (headache becomes pain free) but then recurs after 2 hours, a dose of NSAIDs, acetaminophen, and/or antiemetic drugs may be taken after completion

of the 2 hour assessments of the study drug dose. Triptans, ergots, opioids and barbiturates MUST NOT be used for recurrence medication within 24 hours of study drug administration.

The use of rescue and recurrence medication details will be recorded in the paper diary.

Figure LAIH.2 illustrates allowance period of these restricted rescue and recurrence medications.

[figure not shown]

Figure LAIH.2. Allowance of restricted rescue/ recurrence medications.

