Time to MBS-Free by Chosen Symptom Through 48 Hours Post-Dose: (Nausea, Phonophobia, Photophobia)

This is 3 separate subgroup analysis of “Time to MBS Free Through 48 Hours Post-Dose”. For example, the nausea analysis is based on those who chose “nausea” as the most bothersome symptom at baseline.

Disability

Disability is measured on a four-point scale: not at all (0); mild interference (1); marked interference (2); and need complete bed rest (3). Proportion of patients with score = 0 for each group at each post baseline time point is analyzed. Note that patients with 0 severity at baseline will be excluded from the analysis. In addition, frequency of each category will be summarized.

Incidence of Rescue or Recurrence Medication Use

The analysis is conducted for 3 time frames, depending on rescue or recurrence medication dose time after the treatment intake: [0h<=dose<2h], [2h<=dose<24h], and [24h<=dose<=48h].

A subject is defined to have used rescue or recurrence medication if at least one medication is used during the time frame. Definitions of rescue/recurrence medication are in PROTOCOL Section 7.2.1.1.

Incidence of Headache Recurrence Through 24/48 Hours Post-Dose

It is defined that patients with pain-free at 2 hours post-dose becomes mild (1) or more before or at 24/48 hours post dose. We consider missing data as “non-recurrence” at each time point.

PGI-C

PGI-C is measured on a seven-point scale from “very much better” to “very much worse.” Responder is defined as top two categories, "very much better" and "much better". In addition, frequency of each category will be summarized.

Sustained Pain Free at 24 hours and 48 hours

Sustained Pain-Free is defined as experiencing headache pain-free at two hours after the dose and at the indicated assessment time, having not used any rescue/recurrence medications after the dose up to the assessment timing.

Time to No Disability Through 24 Hours

Disability is measured on a four-point scale: not at all (0); mild interference (1); marked interference (2); and need complete bed rest (3).

No Disability timing is defined as the first time when severity becomes 0. Note that patients with 0 severity at baseline will be excluded from the analysis.

Summary of Symptom-Free at Assessment Times (Nausea, Phonophobia, Photophobia, Vomiting)

This is 4 separate analysis of the symptom.

Total Migraine Freedom

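### The exploratory headache-recurrence variable (SAP 5.6.3, ID 13) has no medication term and counts missing entries as non-recurrence, so relapses resolved or unrecorded at the next diary entry are lost

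*SAP*

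**What the plan says.** SAP 5.6.3 defines the incidence of headache recurrence through 24/48 hours (ID 13 in Table LAIH. 5.3) by severity alone: a patient pain free at 2 hours whose headache "becomes mild (1) or more before or at 24/48 hours post dose". It adds: "We consider missing data as “non-recurrence” at each time point". According to the SAP revision history, the missing-data rule came in with version 2. The table types the variable as exploratory, names ITT as the population, and plans logistic regression.

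Protocol 5.1.3 has patients record their response "at specific postdose time points of 0.5, 1, 1.5, 2, 3, 4, 24, and 48 hours", so after 2 hours the severity entries are at 3, 4, 24 and 48 hours. SAP Appendix 1 shows the same schedule.

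The same protocol section provides that, once the 2-hour assessments are done, patients needing medication "for migraine recurrence (the migraine becomes pain free at 2 hours but then recurs after 2 hours), may take NSAIDs, acetaminophen, and/or antiemetic drugs". Protocol 7.2.1.1 gives the data source: "The use of rescue and recurrence medication details will be recorded in the paper diary". SAP 5.4 bases efficacy analyses on the eDiary unless a definition says otherwise, and the recurrence definition does not.

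Three other SAP rules bear on this:
- Sustained Pain Free (ID 15, secondary) requires that no rescue or recurrence medication was used up to the assessment.
- Rescue or recurrence medication use (ID 12, exploratory) is analysed separately for 0–2, 2–24 and 24–48 hours.
- SAP 5.4.1 makes every evaluation after rescue or recurrence medication a nonresponder, including missing ones.

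**The concern.** The protocol describes recurrence medication as a drug taken because the headache has come back, yet taking it does not make a patient recurrent under ID 13. Take a patient who is pain free at 2 hours, relapses at 8 hours, takes a permitted drug and is pain free at 24 hours. The severity record reads zero at each entry from 2 to 24 hours, and the patient is recorded as non-recurrent. The same patient fails Sustained Pain Free because of that drug. Two tables in one report would then describe the same course differently.

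The missing-data rule adds to this. A patient whose 24-hour entry is absent is given the favourable outcome. Pain free, pain relief and MBS treat missing as non-response, and Modified Sustained Pain Free excludes patients with a missing 24-hour or 48-hour evaluation. The sensitivity analyses in SAP 5.6.2 cover only the primary test, the two key secondary tests and MBS, so nothing planned would show how much the recurrence rate depends on the rule.

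At stake is how low the reported recurrence rate looks. A low rate is a favourable description of an acute migraine drug.

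**Working it through.** The plan states no recurrence rate and no power for recurrence, so there is no figure to reproduce. The check has two parts.

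**1. What the rules record.** For a patient pain free at 2 hours, in the 24-hour analysis:

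| Course after 2 h | ID 13 |
|---|---|
| Pain at a completed 3 h or 4 h entry | recurrence |
| Relapse after 4 h, still present at a completed 24 h entry | recurrence |
| Relapse after 4 h, resolved by 24 h, medicated or not | no recurrence |
| Relapse after 4 h, 24 h entry missing | no recurrence |

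The unobserved interval is 24 − 4 = 20 hours. For the 48-hour analysis there is a second one of 48 − 24 = 24 hours. Both come from the diary schedule; an hour with no scheduled entry is not a missing entry. The schedule makes some relapses invisible in the severity data, and the lack of a medication term means that the treated ones are not recovered from the paper diary.

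**2. Possible size.** Every input here is an assumption:
- R: true 24-hour recurrence rate among 2-hour pain-free patients
- e: share of recurrences that start by 4 hours, with the 3-hour and 4-hour entries taken as complete
- m: share of later recurrences that are medicated
- s, u: probability of being pain free again at 24 hours if medicated, or if not
- q: probability that the 24-hour entry is missing

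Recorded by the SAP = R·e + R·(1−e)·[m(1−s) + (1−m)(1−u)]·(1−q)

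With medication counted = R·e + R·(1−e)·[m + (1−m)(1−u)(1−q)]

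With R = 30%:

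| Scenario | e | m | s | u | q | SAP records | Share of true rate | Medication counted |
|---|---|---|---|---|---|---|---|---|
| A | .3 | .4 | .5 | .2 | .05 | 22.6% | 75% | 27.0% |
| B | .2 | .6 | .7 | .3 | .05 | 16.5% | 55% | 26.8% |
| C | .1 | .8 | .8 | .4 | .10 | 9.8% | 33% | 27.5% |
| No loss | .2 | 0 | 0 | 0 | 0 | 30.0% | 100% | 30.0% |

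Scenario A in full: 0.09 + 0.21 × (0.20 + 0.48) × 0.95 = 0.226. With medication counted: 0.09 + 0.21 × (0.40 + 0.48 × 0.95) = 0.270. The share of the true rate does not depend on R; at R = 20% and 40% it is the same.

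The missing-data rule on its own (e = .2, no medication, no resolution) gives 0.06 + 0.24 × (1 − q): 28.8%, 27.6% and 26.4% at 5%, 10% and 15% missing. In scenarios A to C, most of the loss therefore comes from relapses that resolve before the next entry.

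For scale, the planning numbers in SAP 5.2 imply 190 × 0.213 + 81 × 0.286 + 190 × 0.314 + 163 × 0.388 = 40.5 + 23.2 + 59.7 + 63.2 ≈ 187 patients pain free at 2 hours. Those are mITT counts; the ITT set named for this variable may be somewhat larger. At R = 30%, about 56 recurrences would be recorded as about 42, 31 or 18 in scenarios A, B and C, and as about 50 to 51 if medication counted.

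**The case against.** The strongest reply is SAP 5.4.1. If evaluations after recurrence medication are nonresponder, the patient in the example is not pain free at 24 hours and could be coded as recurrent. This shows that the text can be read two ways, but it does not cure the definition. Section 5.4.1 speaks of response status. It does not say what nonresponder means for an unfavourable event defined by a severity score, and its treatment of missing evaluations after medication pulls against the specific rule in 5.6.3. Two programmers could code the same patient differently.

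The second reply is that the variable is exploratory, is not a protocol objective and lies outside the gatekeeping, while medication use is reported under ID 12 and enters Sustained Pain Free. That is right. It limits the consequence, and the information is not lost to the trial.

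Several stronger readings are tempting, and the documents do not support them:
- A reader might infer that relapses between 4 and 24 hours are never seen. Those still present at a completed 24-hour entry are counted.
- A reader might infer that every choice lowers the rate. The threshold of mild pain works the other way: Modified Sustained Pain Free tolerates mild pain, and ID 13 counts it as recurrence.
- A reader might take ITT in Table LAIH. 5.3 to mean that patients never pain free at 2 hours enter as non-recurrent. The population column does not fix the denominator: Disability is also listed as ITT, yet patients with no disability at baseline are excluded from it, and the recurrence wording starts from 2-hour pain-free patients. If all ITT patients did enter, an equal assumed 30% recurrence in both arms would give 0.30 × 21.3% = 6.4% on placebo and 0.30 × 38.8% = 11.6% on 200 mg, an odds ratio of about 1.9 against lasmiditan.
- A reader might infer that the comparison with placebo is tilted towards lasmiditan. That would depend on how medication use, resolution and missing entries differ between arms, which the documents do not give.

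**Conclusion.** The point holds for the definition of ID 13. A severity-only event with no medication term, together with missing counted as non-recurrence, can only lower the recorded recurrence rate relative to the true one. It loses relapses that have resolved by the next entry, and relapses whose next entry is missing unless a later completed entry in the window still shows pain. It also disagrees with Sustained Pain Free about the same patient, and SAP 5.4.1 leaves the coding unsettled.

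The size cannot be derived from the documents. Under the assumed inputs shown, the recorded rate runs from 33% of the true rate to all of it. There is no loss when nobody is medicated, nothing resolves before the next entry and nothing is missing. Those figures are illustrations, not estimates. The direction of any effect on the comparison between arms is not established.

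The consequence is confined to one exploratory variable. The primary and key secondary tests do not use it.

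**What to change.** Revise the ID 13 entry in SAP 5.6.3 as follows:
- State that the denominator is patients pain free at 2 hours.
- Count a patient as recurrent if severity is 1 or more at any entry after 2 hours, or if rescue or recurrence medication was taken for headache after 2 hours, up to 24 or 48 hours as applicable. Name the medication data as a source alongside the eDiary.
- State how SAP 5.4.1 applies to this variable, so that there is one coding for a medicated patient with a pain-free or missing later entry.
- For unmedicated patients with missing entries, report both bounds: missing as recurrence and missing as non-recurrence.

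The cost is one extra derivation, since medication use is already derived by time window for ID 12, and a less favourable rate. The permitted drugs include antiemetics, so counting medication could over-count if one was taken for nausea alone. The restriction to medication taken for headache is meant to limit that and relies on a usable reason for use. Where the reason is unclear, a listing of the affected patients would show how many depend on it. Relapses that are untreated and resolved before the next entry stay unobserved under this diary schedule, and the report should say so.

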- Sec.5.6.1 (Primary and Key Secondary Analysis): "Summary of Characteristics of Treated Migraine (at onset of dosing)" was added.
- Sec.5.6.2 (Sensitivity Analysis): "Remove patients who took the dose with baseline mild severity in mITT population" was deleted because such patients would be excluded in mITT after modifying the mITT condition in SAP version 2.
- Sec.5.6.2 (Sensitivity Analysis): "Include patients who recorded the baseline measurement in eDiary after taking the dose and who has 2 hours assessment" was deleted because such patients would be included in mITT after modifying the mITT condition in SAP version 2.
- Sec.5.6.2 (Sensitivity Analysis): [T1] specific sensitivity analysis was added. Estimation methods for response rate using logistic regression was added.
- CCI [REDACTED]

- Sec. 5.6.3 (Details of Efficacy Analyses): For Disability and PGI-C analysis, summary table will be created.
- Sec. 5.6.3 (Details of Efficacy Analyses): The name of the analysis "Incidence of Headache Recurrence Through 48 Hours Post-Dose" was modified to "Incidence of Headache Recurrence Through 24/48 Hours Post-Dose." The definition of missing data case was added.
- Sec. 5.6.3 (Details of Efficacy Analyses): The definition and analysis of "Summary of Symptom-Free at Assessment Times (Nausea, Phonophobia, Photophobia, Vomiting)" (ID=17) was added.
- Sec. 5.6.3 (Details of Efficacy Analyses): In Table LAIH. 5.3, for "Time to Meaningful Pain Relief Through 48 Hours" and "Time to Pain Free Through 48 Hours", 6 hours and 8 hours results were added.
- Sec. 5.6.3 (Details of Efficacy Analyses): Following analyses were deleted because they would be less important.
 - Relative migraine freedom (original ID=17)
 - EQ-5D-5L responder analysis (original ID=22)
 - Pain Relief at 24 Hours and 48 Hours with Pain Relief at 2 Hours (original ID= 27)
 - Pain Free at 24 Hours and 48 Hours with Pain Relief at 2 Hours (original ID= 28)

- Sec. 5.6.3 (Details of Efficacy Analyses): Modified sustained pain freedom: The definition of missing data is modified to align with other historical data of triptans. In the new definition, if the data is missing, then it is excluded from the responder analysis instead of setting it as non-responder.
- Sec. 5.6.3 (Details of Efficacy Analyses): For Treatment Satisfaction, “Distribution of responses and proportion of patients with agree or strongly agree” was added.

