5.4.1. Handling of Missing Values

Subjects who fail to record information at an analysis time point will have that value considered missing in the respective table (hence, no imputation), unless otherwise specified.

Pain free, Pain relief, and MBS analysis are exceptions to this. Missing value at a particular time point is considered as “non-responder.”

Note that if a patient takes a rescue/recurrent medication at some postbaseline timepoint (see Section 5.4), then all evaluation after that timepoint becomes nonresponder, even if the evaluation is missing.

For time-to-event analyses (Time to Meaningful Pain Relief Through 48 Hours, Time to Pain Free Through 48 Hours), patients will be censored at the first time when rescue/recurrent medication are used or at 48 hours, whichever the earliest.

For the other time-to-event analyses (Kaplan-Meier analyses), the patient will be censored at the first missing evaluation time point or rescue/recurrent medication taken time (postbaseline), or the last possible evaluation point whichever the earliest, unless otherwise specified. For example, the last possible evaluation point of disability is at 24 hours.

A sensitivity analysis for missing data will be performed. (See Section 5.6.2).

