If patients are pain free and are not experiencing any other migraine symptoms (i.e. nausea, photophobia, phonophobia, or vomiting), then they are total migraine free.

Modified Sustained Pain Free at 24 hours and 48 hours

Modified Sustained Pain-Free is defined as experiencing headache pain-free at two hours after the dose and no moderate or severe pain at the indicated assessment time, having not used any medications to treat migraine after the dose up to the assessment timing. Note that if a patient has missing evaluation at 24 hours, then he is excluded from the analysis instead of setting his response as nonresponder. The same is true at 48 hours evaluation.

Time to Meaningful Pain Relief Through 48 Hours

Meaningful Pain Relief timing is defined as the time when the corresponding eDiary question is answered as Yes.

Time to Pain Free Through 48 Hours

Pain Free timing is defined as the time when the corresponding eDiary question is answered as Yes.

Change from Baseline of EQ-5D-5L in Index Score

It is based on the EQ-5D Health Status Index Score. The Japan specific tariffs (Japanese population-based index value) for the EQ-5D Health Status Index Score is used. Change from baseline is based on Baseline (0 hour) and post-baseline (24 hours).

Change from Baseline of EQ-5D-5L in Visual Analog Scale

The change of EQ-5D-5L visual analog scale is based on Baseline (0 hour) and post-baseline (24 hours) from the onset of dosing.

HRQoL Measured by MQoLQ in 5 Domains

There are 5 domains in MQoLQ. Each domain will be analyzed separately: work functioning, social functioning, energy and vitality, feelings and concerns, and migraine symptoms. Each domain consists of 3 questions answered on a 7-point scale where 1 indicates maximum impairment and 7 indicating no impairment. A domain score is calculated by summing the responses to the 3 questions and the domain score ranges from 3 to 21. The response variable in this analysis is raw values at 24 hours.

Treatment Satisfaction

There are 4 questions. Each question will be analyzed separately. Distribution of responses and proportion of patients with agree or strongly agree will be summarized for each treatment group:

- the patient's level of satisfaction (ranging from extremely dissatisfied to extremely satisfied)
- their willingness to take this treatment again (ranging from strongly disagree to strongly agree)

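### Exploratory Modified Sustained Pain Free (ID 19) drops patients already known to have failed when the 24 h or 48 h entry is missing; for rescue/recurrence users this conflicts with SAP 5.4.1

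*SAP*

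**What the plan says.** SAP 5.6.3 defines Modified Sustained Pain Free by three conditions. The first two are "experiencing headache pain-free at two hours after the dose and no moderate or severe pain at the indicated assessment time". The third is "having not used any medications to treat migraine after the dose up to the assessment timing". On missing data it says that "if a patient has missing evaluation at 24 hours, then he is excluded from the analysis instead of setting his response as nonresponder", and then "The same is true at 48 hours evaluation". It makes no exception for a patient who has already failed one of the other conditions.

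SAP 5.4.1 sets the general rules. By default a missing value "will have that value considered missing in the respective table (hence, no imputation), unless otherwise specified". Then "Pain free, Pain relief, and MBS analysis are exceptions to this": for those endpoints a missing value counts as non-response. A separate sentence covers patients who take rescue or recurrence medication: "then all evaluation after that timepoint becomes nonresponder, even if the evaluation is missing".

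The SAP revision history (Section 3) shows that both the rescue sentence and the exclusion rule came in with version 2. The reason given for the exclusion is: "The definition of missing data is modified to align with other historical data of triptans".

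Table LAIH. 5.3 lists the endpoint as ID 19, exploratory, ITT, analysed by logistic regression. The secondary endpoint Sustained Pain Free (ID 15) carries no such exclusion.

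**The concern.** Failing at 2 hours, or taking migraine medication, settles the outcome whatever the later entry would have shown. Nothing about that patient's response is missing, yet the rule treats the patient as unknown. Medication use can be documented without the later entry: under Protocol 9.1.1 headache severity goes into the eDiary, while under Protocol 5.1.3 and 7.2.1.1 rescue and recurrence medication goes into a paper diary.

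Two things are at stake. First, a rescue user with no 24 h entry is a nonresponder under 5.4.1 and excluded under 5.6.3, so two programmers following the SAP could produce different denominators. Second, the stated purpose is alignment with historical triptan data, where the absolute rate matters, and that rate depends on how many known failures are removed. Nothing planned would show the effect, because the missing-data sensitivity analysis in SAP 5.6.2 covers only [T1], [T2], [T3] and MBS.

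**Working it through.** **Figures in the plan.** The documents give no rate, missing-data proportion or rescue-use proportion for this endpoint, so there is no stated figure to reproduce. The 2 h pain-free rates come from SAP 5.2: 21.3% for placebo and 38.8% for 200 mg. As a check on those inputs, the stated power reproduces to within 2 points: [T1] 95.0% (stated 93.6%), [T2] 94.9% (94.9%), [T3] 92.2% (91.2%), joint 86.8% (85.6%).

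**Assumptions (not in the documents).** The share of 2 h pain-free patients who sustain is s = 0.60. The proportion missing the later entry is f = 0.10 to 0.20 among 2 h failures and r = 0.03 to 0.05 among 2 h pain-free patients.

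**Formulas**, with q the 2 h pain-free rate:

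- Plan: q·s·(1−r) / [q(1−r) + (1−q)(1−f)]
- Known failures kept: q·s·(1−r) / [q(1−r) + (1−q)]
- All missing as nonresponder: q·s·(1−r)
- Complete data: q·s

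Only 2 h failures count as known failures here. Patients pain free at 2 h who took medication and then missed the entry would also be kept under the fix, which would lower the kept rate a little further.

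**Worked case, 200 mg, f = 0.20, r = 0.03.** The numerator is 0.388 × 0.60 × 0.97 = 0.2258. The plan's denominator is 0.388 × 0.97 + 0.612 × 0.80 = 0.8660, giving 26.1%. The kept denominator is 0.3764 + 0.612 = 0.9884, giving 0.22848, or 22.8%. Complete data give 0.388 × 0.60 = 23.3%.

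**All four corners:**

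| f | r | Placebo: plan | Placebo: kept | 200 mg: plan | 200 mg: kept |
|---|---|---|---|---|---|
| 0.10 | 0.03 | 13.5% | 12.5% | 24.4% | 22.8% |
| 0.10 | 0.05 | 13.3% | 12.3% | 24.1% | 22.6% |
| 0.20 | 0.03 | 14.8% | 12.5% | 26.1% | 22.8% |
| 0.20 | 0.05 | 14.6% | 12.3% | 25.8% | 22.6% |

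Complete data give 12.8% for placebo (0.213 × 0.60). Counting all missing as nonresponse gives 12.1% to 12.4% for placebo and 22.1% to 22.6% for 200 mg.

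**Treatment comparison.** With f = 0.20 and r = 0.03 the plan's odds ratio is (0.2608/0.7392) / (0.1482/0.8518) = 2.03. Over the four corners it is 2.03 to 2.06 under the plan and 2.08 with known failures kept, against 2.07 with complete data. The risk difference is 10.7 to 11.3 points under the plan, 10.3 to 10.4 with known failures kept, and 10.5 with complete data.

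**Equal missingness.** Take s = 0.70 and 10% missing in both groups. The plan gives 14.9% and 27.2% (placebo, 200 mg), the same as complete data. Keeping known failures gives 13.7% and 25.4%; all missing as nonresponder gives 13.4% and 24.4%. In this case the excluded patients split as the 2 h outcome does, so 78.7% of those excluded on placebo (1 − 0.213) and 61.2% on 200 mg (1 − 0.388) are known failures.

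**Wider range.** With s from 0.5 to 0.9, missingness of 5% to 20% in 2 h pain-free patients and 0% to 20% in 2 h failures, the plan's rate exceeds the kept rate by 0 to about 5 points.

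**The case against.** The strongest reply is that this was a deliberate choice on a minor endpoint. The exclusion is written out for this endpoint, its reason is recorded, and version 2 was approved before unblinding. The endpoint appears neither among the protocol objectives nor in SAP Table LAIH. 4.1, and it lies outside the sequential tests. The historical triptan definitions are not in the documents, so one cannot say that the rule fails its purpose. All of this stands, and it is why the current rule should be kept as a labelled analysis.

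A reader might infer that the exclusion contradicts Section 5.4.1 as a whole. The documents do not support that. For a 2 h failure who took no medication, the rescue sentence does not apply, and 5.6.3 expressly replaces the general treatment of missing pain-free data. The specific-over-general argument is weaker for rescue/recurrence users. The 5.4.1 allowance for rules specified elsewhere is attached to the no-imputation default, not to the rescue sentence. Both rules entered in the same version, so neither supersedes the other by date.

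A reader might also infer that the rule inflates the response rate outright. That is certain only against counting known failures. Against the true rate it depends on who is missing, which the documents do not say; with equal missingness the plan's rate is unbiased and the fix understates it.

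**Conclusion.** The point holds in limited form. For ID 19 the SAP discards patients whose failure is already determined, and for rescue/recurrence users with a later missing entry 5.4.1 and 5.6.3 give different results with no stated precedence. That conflict rests on the text alone; how many patients it touches cannot be derived from the documents.

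The size is conditional. Under the assumed inputs, where failures are missing more often, the plan's rate exceeds the known-failures-kept rate by 1.5 to 3.2 points on 200 mg and 1.1 to 2.3 points on placebo. It exceeds the complete-data rate by 0.8 to 2.8 and 0.6 to 2.0 points respectively.

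A distorted treatment comparison should not be inferred. If missingness depends only on 2 h status, the odds ratio moves by about 0.05 at most, and under the inputs above the plan's odds ratio is slightly below the complete-data value. [T1] to [T3], their power, the sequential testing and the secondary endpoint Sustained Pain Free are unaffected.

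**What to change.** In SAP 5.6.3, under Modified Sustained Pain Free:

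- State that a patient not pain free at 2 h, or who used migraine medication before the time point, is a nonresponder even if the 24 h or 48 h entry is missing, so that 5.4.1 governs rescue/recurrence users.
- Exclude only patients whose outcome is undetermined: pain free at 2 h, no migraine medication, later entry missing.
- Add a version that counts every missing entry as nonresponse.
- Keep the current version, with all missing entries excluded, as a labelled analysis for the historical triptan comparison.

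The cost is a sentence or two, one derivation change and two additional labelled outputs. The downside is a slightly less favourable rate that understates the true rate if missingness is unrelated to outcome: in the equal-missingness example, 13.7% against 14.9% on placebo and 25.4% against 27.2% on 200 mg. Showing the versions side by side lets the reader judge that.
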